## 4.6. Benefit:Risk Assessment

Summaries of findings from both clinical and non-clinical studies conducted with mepolizumab (SB-240563) lyophilised drug product can be found in the Investigator's Brochure [GSK Document Number CM2003/00010/12]. The following section outlines the key risks, risk assessment and mitigation strategy for this protocol based on mepolizumab lyophilised formulation. The safety profile of the mepolizumab liquid formulation is anticipated to be similar to the lyophilised formulation.

## 4.6.1. Risk Assessment

Potential Risk of Clinical Significance	Summary of Data/Rationale for Risk	Mitigation Strategy
	Investigational Product (IP)	
Risk of Systemic Reactions including allergic reactions	
 
Biopharmaceutical products administered subcutaneously may elicit systemic (e.g. hypersensitivity) and local site reactions.
 
In the placebo controlled severe asthma studies both acute and delayed systemic reactions including hypersensitivity have been reported following administration of mepolizumab with incidence rates similar between mepolizumab and placebo-treated subjects:
 
54/915 subjects or 6% in the mepolizumab [all doses combined] group
 
7/263 subjects or 3% in the mepolizumab 100 mg SC group
 
12/344 subjects or 3% in the mepolizumab 75 mg intravenous (IV) group
 
20/412 subjects or 5% in the placebo group.
 
The most common symptoms reported with any systemic reaction included headache, rash, pruritus, fatigue, and dizziness. While
 
	
 
Daily monitoring of serious adverse events (SAEs) by medical monitor; regular systematic review of adverse event (AE)/SAE data from ongoing studies by the GSK study team and/or safety review team.
 
Customised AE and SAE case report form (CRF) utilised for targeted collection of information for systemic reaction adverse events.
 
Use of Joint National Institute of Allergy and Infectious Disease (NIAID)/Food Allergy and Anaphylaxis Network (FAAN) 2nd Symposium on Anaphylaxis to collect data on reports of anaphylaxis (see Appendix 2 ).
 
Subjects are monitored in clinic for at least 1 hour following self-administration of mepolizumab at the clinic. For administration at home, subjects will be instructed to call the investigator and/or go to an Emergency Department for any unusual symptoms (e.g. symptoms
 

Potential Risk of Clinical Significance	Summary of Data/Rationale for Risk	Mitigation Strategy
	rare, serious systemic reactions including anaphylaxis have been reported. Systemic reactions reported to date across the mepolizumab programme are summarized in the IB "Adverse Events of Special Interest" section; see also 'Special Warnings and Special Precautions for Use' section located in Section 6 titled 'Summary of Data and Guidance for the Investigator' [GSK Document Number CM2003/00010/12].	concerning for hypersensitivity include skin rash [hives] or redness, swelling of the face or mouth, becoming wheezy, coughing or having difficulty in breathing and/or feeling weak or light headed).
Injection site reactions	In the placebo controlled severe asthma (PCSA) studies the incidence of local site reactions with SC administration of mepolizumab was higher on mepolizumab 100 mg SC group (21/263 or 8%) compared to mepolizumab 75mg IV (10/344 or 3%) or placebo (13/412 or 3%). Symptoms included pain, erythema, swelling, itching, and burning sensation. Local injection site reactions reported to date across the mepolizumab program are summarized in the IB "Adverse Events of Special Interest" section; see also Section 6 titled 'Summary of Data and Guidance for the Investigator' [GSK Document	
 
Daily monitoring of serious adverse events (SAEs) by medical monitor; regular systematic review of adverse event (AE)/SAE data from ongoing studies by GSK study team and/or safety review team.
 
Customised AE and SAE case report form (CRF) utilised for targeted collection of information for local injection site reaction adverse events.
 
Pain assessment will also be done utilizing visual analog scale, in the patient diary, immediately after injection, 1 hour after injection.
 

Potential Risk of Clinical Significance	Summary of Data/Rationale for Risk	Mitigation Strategy
	Number CM2003/00010/12].	
Potential risk of immunogenicity	
 
Biopharmaceutical products may elicit anti- drug antibody (ADA) and neutralising antibody (NAb), which have the potential to modulate pharmacokinetic (PK), pharmacodynamic (PD) or produce adverse reactions.
 
Mepolizumab has low immunogenic potential. Both incidence and titer data from completed studies demonstrate a low risk for loss of efficacy associated with AEs and/or altered PK/PD. Immunogenicity data reported to date across the mepolizumab development program are summarized in the IB; See Section 5.4 'Clinical Immunogenicity' and a summary of immunogenicity findings in Section 6 'Other Potentially Clinically Relevant Information for the Investigator' [GSK Document Number CM2003/00010/12].
 
	Blood samples will be collected for detection of both ADA and NAb.
	Study Procedures	
Injuries due to accidental needle sticks	The autoinjector has been designed and verified to comply with ISO23908 'Sharps injury protection – Requirements and test methods – Sharps protection features for single-use hypodermic needles, introducers for catheters and needles used for blood	The subject will be educated by the staff prior to self-administration and their first scheduled dose will be supervised in the clinic by the staff. Additionally, the IFU will instruct the subject on the safe use of

### 2016N275054\_04

### CONFIDENTIAL

Potential Risk of Clinical Significance	Summary of Data/Rationale for Risk	Mitigation Strategy
	sampling'	the device.
		A plastic needle cover shields the needle before and after injection to minimise the potential for needle stick injuries.
		The needle is protected by a guard, which following injection, re-extends and locks in place to cover the needle.

## 4.6.2. Benefit Assessment

The primary purpose of this study is to assess the appropriate use of the autoinjector in a real world use setting. Participants are intended to be broadly representative of patients and caregivers (i.e., similar age, dexterity and cognitive abilities, degree of training or experience with an autoinjector) who may use the autoinjector, either for the treatment of severe eosinophilic asthma or, potentially, other approved indications. Efficacy is not being assessed in this study as the efficacy of mepolizumab in severe eosinophilic asthma has previously been demonstrated in prior studies [Haldar, 2009; Nair, 2009; Pavord, 2012; Bel, 2014; Ortega, 2014]. The autoinjector is intended to provide a more convenient mode of delivery from previous mepolizumab administration and potentially gives patients an option to self-administer mepolizumab at home.

## 4.6.3. Overall Benefit:Risk Conclusion

Current data from mepolizumab preclinical and clinical development indicate the ability of mepolizumab to inhibit IL-5 leading to consistent reduction in blood eosinophils, with demonstration of clinical benefit in the treatment of conditions associated with eosinophilic inflammation, such as asthma. Data from the Phase III asthma programme with mepolizumab demonstrates, compared to placebo, a reduction in asthma exacerbations, improvements in asthma control and quality of life (as measured by the ACQ and SGRQ, respectively), improvements in lung function and a reduction in oral corticosteroid use in those subjects on chronic OCS treatment. To date, the safety profile of mepolizumab has been favourable and the benefit/risk profile remains positive in patients with severe asthma. The change in drug product presentation from a lyophilised drug product to a liquid drug product in an autoinjector is not anticipated to alter the overall benefit:risk. The ability of subjects to self-administer treatment will be closely observed in the clinic and subjects will be instructed to seek medical attention if they experience any abnormal symptoms following administration at home, away from the clinic.

# 5. SELECTION OF STUDY POPULATION AND WITHDRAWAL CRITERIA

Specific information regarding warnings, precautions, contraindications, adverse events, and other pertinent information on the GSK investigational product or other study treatment that may impact subject eligibility is provided in the IB/IB supplement(s).

Deviations from inclusion and exclusion criteria are not allowed because they can potentially jeopardise the scientific integrity of the study, regulatory acceptability or subject safety. Therefore, adherence to the criteria as specified in the protocol is essential.

## 5.1. Inclusion Criteria

A subject will be eligible for inclusion in this study only if all of the following criteria apply:

### AGE

1. Age: At least 12 years of age inclusive, at the time of signing the informed consent. [For those countries where local regulations permit enrolment of adults only, subject recruitment will be restricted to those who are  $\geq 18$  years of age]

### TYPE OF SUBJECT AND DIAGNOSIS INCLUDING DISEASE SEVERITY

### 2. Asthma: A physician diagnosis of asthma for ≥2 years that meets the National Heart, Lung and Blood Institute guidelines [National heart, lung and blood institute (NIH), 2007] or Global Initiative for Asthma (GINA) guidelines [GINA, 2015]

## 3. Mepolizumab treatment:

a. Not receiving mepolizumab treatment at Visit 1 (NB: these subjects must also meet inclusion criteria 4, 5, 6 and 7).

### OR

b. Receiving 100 mg SC mepolizumab administered for the treatment of severe eosinophilic asthma every 4 weeks for at least 12 weeks prior to Visit 1.

# The following inclusion criteria are only applicable to those subjects NOT receiving mepolizumab treatment at Visit 1:

- 4. **Eosinophilic asthma**: A high likelihood of eosinophilic asthma as per the required 'Continuation to Treatment' Criterion 2.
- 5. **Inhaled Corticosteroid:** A well-documented requirement for regular treatment with high dose inhaled corticosteroid (ICS) in the 12 months prior to Visit 1 with or without maintenance oral corticosteroids (OCS).
  - For subjects  $\geq 18$  years old:
    - ICS dose must be ≥880 mcg/day fluticasone propionate (FP) (exactuator) or equivalent daily.
    - For ICS/long-acting-beta-2-agonist (LABA) combination preparations, the highest strength approved maintenance dose in the local country will meet this ICS criterion.

• For subjects  $\geq 12$  to  $\leq 17$  years old:

- ICS dose must be  $\geq$ 440 mcg/day FP (ex-actuator) or equivalent daily.
- For ICS/LABA combination preparations, the mid-strength approved maintenance dose in the local country will meet this ICS criterion.

(Subjects will be permitted to be enrolled without continuous high dose ICS providing the subject was receiving continuous ICS and the Investigator attests that the subject should have been treated with high dose ICS to mitigate the risk of exacerbations but financial or tolerance issues prevented the use of high-dose ICS. Such subjects should be discussed with GSK Medical Monitor prior to enrolment)

- 6. **Controller Medication:** Current treatment with an additional controller medication, besides ICS, for at least 3 months or a documented failure in the past 12 months of an additional controller medication [e.g., long-acting beta-2-agonist (LABA), leukotriene receptor antagonist (LTRA), or theophylline] for at least 3 successive months.
- 7. **Exacerbation history:** Previously confirmed history of one or more exacerbations requiring treatment with systemic corticosteroid (CS) [intramuscular (IM), intravenous, or oral] in the 12 months prior to Visit 1, despite the use of high-dose ICS. For subjects receiving maintenance CS, the CS treatment for an exacerbation must have been a two-fold dose increase or greater.

### WEIGHT

8. Body weight: A minimum  $\geq$ 40 kg at Visit 1

### SEX

9. Gender: Male or Female

### Females:

A female subject is eligible to participate if she is not pregnant (as confirmed by a negative urine human chorionic gonadotrophin (hCG) test), not planning to become pregnant during the time of study participation (and up to 16 weeks after the last dose), not lactating, and at least one of the following conditions applies:

a. Non-reproductive potential defined as:

• Pre-menopausal females with one of the following:

- Documented tubal ligation
- Documented hysteroscopic tubal occlusion procedure with follow-up confirmation of bilateral tubal occlusion
- Hysterectomy
- Documented Bilateral Oophorectomy
- Postmenopausal female (see Appendix 3 for specific criteria).
- b. Reproductive potential and agrees to follow one of the options listed in the Modified List of Highly Effective Methods for Avoiding Pregnancy in Females of Reproductive Potential (FRP) (see Appendix 3) from 30 days prior to the first dose of study medication and until 16 weeks after the last dose of study medication and completion of the End of Study/Early Withdrawal visit.

The investigator is responsible for ensuring that subjects understand how to properly use these methods of contraception.

### INFORMED CONSENT

10. **Informed Consent:** Capable of giving signed informed consent which includes compliance with the requirements and restrictions listed in the consent form and in this protocol.

## 5.2. Exclusion Criteria

A subject will not be eligible for inclusion in this study if any of the following criteria apply:

CONCURRENT CONDITIONS/MEDICAL HISTORY (INCLUDES LIVER FUNCTION AND QTc INTERVAL)

- 1. **Concurrent Respiratory Disease:** Presence of a known pre-existing, clinically important lung condition other than asthma. This includes current infection, bronchiectasis, pulmonary fibrosis, bronchopulmonary aspergillosis, or diagnoses of emphysema or chronic bronchitis (chronic obstructive pulmonary disease other than asthma) or a history of lung cancer.
- 2. **Eosinophilic Diseases:** Subjects with other conditions that could lead to elevated eosinophils such as Hypereosinophilic Syndromes, including Churg-Strauss Syndrome, or Eosinophilic Esophagitis. Subjects with a known, pre-existing parasitic infestation within 6 months prior to Visit 1 are also to be excluded.
- 3. **Malignancy:** A current malignancy or previous history of cancer in remission for less than 12 months prior to screening (Subjects that had localized carcinoma of the skin which was resected for cure will not be excluded).
- 4. **Immunodeficiency:** A known immunodeficiency (e.g. human immunodeficiency virus HIV), other than that explained by the use of corticosteroids taken as therapy for asthma.
- 5. **Other Concurrent Medical Conditions:** Subjects who have known, pre-existing, clinically significant cardiovascular, endocrine, autoimmune, metabolic, neurological, renal, gastrointestinal, hepatic, haematological or any other system abnormalities that are uncontrolled with standard treatment.
- 6. Liver Disease: Known, pre-existing, unstable liver disease (as defined by the presence of ascites, encephalopathy, coagulopathy, hypoalbuminaemia, esophageal or gastric varices or persistent jaundice), cirrhosis, and known biliary abnormalities (with the exception of Gilbert's syndrome or asymptomatic gallstones).
- ECG Assessment: QT interval corrected for heart rate by either Fridericia's or Bazett's formula QTc(F)/QTc(B) ≥450msec or QTc(F)/QTc(B) ≥480 msec for subjects with Bundle Branch Block at Visit 1.

### CONCOMITANT MEDICATIONS

8. Xolair: Subjects who have received omalizumab within 130 days of Visit 1.

- 9. **Other Monoclonal Antibodies not including mepolizumab:** Subjects who have received any monoclonal antibody (other than Xolair) to treat inflammatory disease within 5 half-lives of Visit 1.
- 10. **Investigational Medications:** Subjects who have received treatment with an investigational drug, other than mepolizumab within the past 30 days or five terminal phase half-lives of the drug whichever is longer, prior to visit 1 (this also includes investigational formulations of marketed products) or experimental anti-inflammatory drugs (non biologicals) in the past 3 months.
- 11. **Chemotherapy:** Subjects who have received chemotherapy within 12 months prior to Visit 1.

### RELEVANT HABITS

12. Alcohol/Substance Abuse: A history (or suspected history) of alcohol misuse or substance abuse within 2 years prior to Visit 1.

### CONTRAINDICATIONS

13. **Hypersensitivity:** Subjects with hypersensitivity to mepolizumab or to any of the excipients (sodium phosphate, citric acid, sucrose, EDTA, polysorbate 80).

### DIAGNOSTIC ASSESSMENTS AND OTHER CRITERIA

14. Adherence: Subjects who have known evidence of lack of adherence to controller medications and/or ability to follow physician's recommendations.

## 5.3. Continuation to Treatment Criteria

At Visit 2, those subjects who continue to meet the inclusion/exclusion criteria and who meet the continuation to treatment criteria will commence the study treatment phase until the target of approximately 158 enrolled subjects is reached.

In order to receive study treatment subjects must have fulfilled all inclusion and exclusion criteria described in Section 5.1 and Section 5.2. In addition to the following:

### REQUIRED CRITERIA TO START TREATMENT

- 1. **Liver Function:** At Visit 2, ALL study subjects must fulfil the following additional criteria in order to be eligible for study treatment:
  - Liver Function Tests: obtained at Visit 1:
    - Alanine aminotransferase (ALT) $\leq 2x$  ULN (upper limit of normal)
    - Bilirubin ≤1.5x ULN (isolated bilirubin >1.5x ULN is acceptable if bilirubin is fractionated and direct bilirubin <35%)

- 2. **Eosinophilic Phenotype**: At Visit 2, study subjects that were **NOT** receiving mepolizumab treatment at Visit 1 must fulfil the following additional criteria in order

to be eligible for study treatment:

- Airway inflammation characterised as eosinophilic in nature as indicated by one of the following:
  - a) A peripheral blood eosinophil count of  $\geq$ 300 cells/µL that is related to asthma demonstrated in the past 12 months prior to Visit 1.

OR

b) A peripheral blood eosinophil count of  $\geq 150$  cells/µL at Visit 1 that is related to asthma.

## 5.4. **Pre-Screening/Screening Failures**

A subject will be assigned a subject number at the time the informed consent is signed.

A subject who is assigned a subject number at Visit 0 but does not have any screening Visit 1 procedures will be considered a pre-screen failure.

Screen failures will be defined as those subjects who complete at least one Visit 1 (Screening) procedure but do not attempt to self-administer a dose of mepolizumab.

The following information will be collected in the electronic case report (eCRF) for subjects who are pre-screen, and screen failures:

- Date of Informed Consent Form (ICF) signature
- Demographic information including race, age and gender
- Child bearing status assessment for all female subjects of reproductive potential
- Subject number
- Details of asthma medications within 3 months of the pre-screening Visit 0
- Details of asthma exacerbations during the pre-screening period
- Serious Adverse Event information only for any SAE considered as related to study participation (e.g. protocol mandated procedures, invasive tests or change in existing therapy) or related to a GSK concomitant medication
- Investigator signature page

In order to ensure transparent reporting of screen failure subjects, meet the Consolidated Standards of Reporting Trials (CONSORT) publishing requirements, and respond to queries from Regulatory authorities, a minimal set of screen failure information is required including Demography, Screen Failure details, Eligibility Criteria, and Serious Adverse Events (see Section 7.7.1).

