# 6.7. Training Session

Training of study treatment, handling and administration techniques by qualified study site personnel will be provided to the study participants at Visit 2, prior to self-administration. The training is designed to be representative of the instruction and training materials that will be used in the post-marketing setting. The training will consist of a walk-through of the IFU for the injection devices by the site personnel. The first injection will then be observed by site personnel and may include feedback to the subject as needed.

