## 4. ANALYSIS POPULATIONS

Population	Definition / Criteria	Analyses Evaluated
All Subjects Enrolled (ASE)	
 
All subjects for whom a record exists in the data base.
 
	
 
Pre-screen and screen failures
 

All Subjects (Safety)	
 
All enrolled subjects attempting at least one self-administration of mepolizumab.
 
	
 
Endpoints relating to autoinjector use and functionality, including primary endpoint
 
Study Population
 
Safety
 

Pharmacokinetic (PK)	
 
All enrolled subjects attempting at least one self-administration of mepolizumab for whom a PK sample was obtained and analysed.
 
	
 
PK
 

Pharmacodynamic (PD)	
 
All enrolled subjects attempting at least one self-administration of mepolizumab who had a baseline PD measurement and at least one post-treatment PD measurement.
 
	
 
PD
 

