## 7. ANALYSES TO EVALUATE AUTOINJECTOR

- All analyses will be based on the “All Subjects (Safety)” population.
- All analyses to evaluate the autoinjector will be reported separately for the group of subjects using autoinjectors with labelling that includes a pictogram plus standard labelling elements, and the group of subjects using the standard labelling without the pictogram. No comparison between the labels will be performed.

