### 7.1. Primary Analysis

The primary endpoint is the proportion of subjects successfully able to self-administer their observed third dose at Week 8.

- The number and percentage of subjects successfully able to self-administer their observed third dose at Week 8 will be summarized together with 95% CI.
- The denominator for the percentage calculation will be the number of subjects attempting an injection at Week 8.
- CI for the percentages will be generated using the Exact (Clopper-Pearson) method for binomial proportions.
- No formal statistical analysis will be conducted and no comparison between labels will be performed.
- If a subject has more than one attempt to self-administer study treatment at Week 8, the first attempt will be included in the primary analysis. The best attempt will also be summarised as a supportive analysis. A separate listing of injection success for subjects who had more than one attempt to self-administer mepolizumab will be provided.
- If there are withdrawals from study treatment due to issues pertaining to the use of the autoinjector, a sensitivity analysis of the primary endpoint will be performed. Missing injection success assessments for subjects withdrawing from study treatment due to issues with the autoinjector will be included in the analysis as injection failures i.e. as unsuccessful attempts to self-administer mepolizumab. Injection success assessments classed as “not attempted” on the eCRF for subjects withdrawing from study treatment due to issues with the autoinjector will also be included in this analysis as injection failures.

Full details of data displays being presented in [Appendix 8: List of Data Displays](#).

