### 7.2. Secondary Analyses

The following endpoints will be summarised in the same way as the primary endpoint (Section [7.1](#)).

- The number and percentage of subjects successfully able to self-administer their unobserved second dose at Week 4. The denominator for the percentage calculation will be the number of subjects attempting an injection at Week 4.
- The number and percentage of subjects successfully able to self-administer their observed first dose at Week 0. The denominator for the percentage calculation will be the number of subjects attempting an injection at Week 0.
- The number and percentage of subjects successfully able to self-administer both their unobserved second dose at Week 4 and their observed third dose at Week 8. The denominator for the percentage calculation will be the number of subjects attempting an injection at both Week 4 and Week 8.
- The number and percentage of subjects successfully able to self-administer all three doses at Week 0, 4 and 8. The denominator for the percentage calculation will be the number of subjects attempting all three doses at Week 0, 4 and 8.

Data collected on the observer checklist for in-clinic injections and subject completed checklists for home injections will be summarised. The investigator assessment of user/device errors will be summarised by visit. Device usability/functionality assessed by the subject at the end of the study will also be summarised.

Full details of data displays being presented in [Appendix 8: List of Data Displays](#).

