## 14.5. Appendix 5: Reporting Standards for Missing Data

### 14.5.1. Premature Withdrawals

Element	Reporting Detail
General	
 
• Subject study completion is defined as completion of the End of Study (Week 12) visit.
 
• Withdrawn subjects will not be replaced in the study.
 
• All available data from subjects who were withdrawn from the study will be listed and all available planned data will be included in summary tables and figures, unless otherwise specified.
 

Pre-Screen and Screen Failures	
 
• A subject will be assigned a subject number at the time when the informed consent form (ICF) is signed.
 
• A subject who is assigned a subject number but does not have any screening procedures at Visit 1 will be considered a pre-screen failure.
 
• A subject who completes at least one Visit 1 procedure but does not attempt to self-administer a dose of mepolizumab will be considered a screen failure.
 

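### Eligible, trained subjects who decline the first injection because of the autoinjector become screen failures, so even the device-related sensitivity analysis omits them

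*Protocol*

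**What the plan says.** **Screen failure.** Protocol 5.4 applies the term to subjects "who complete at least one Visit 1 (Screening) procedure but do not attempt to self-administer a dose of mepolizumab". SAP 14.5.1 says the same: a subject with a Visit 1 procedure who "does not attempt to self-administer a dose of mepolizumab will be considered a screen failure". Neither text requires that an entry or continuation criterion was failed.

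**Timing.** Continuation criteria are applied at Visit 2 (Protocol 5.3). Training "will be provided to the study participants at Visit 2, prior to self-administration" (Protocol 6.7). A subject can therefore be eligible and trained without yet having attempted a dose.

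**Population.** SAP 4 defines All Subjects (Safety) as "All enrolled subjects attempting at least one self-administration of mepolizumab", in line with Protocol 9.3.1. For the device analyses, SAP 7 states: "All analyses will be based on the “All Subjects (Safety)” population".

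**Denominators.** SAP 7.1: "The denominator for the percentage calculation will be the number of subjects attempting an injection at Week 8". SAP 7.2, for the first dose: "The denominator for the percentage calculation will be the number of subjects attempting an injection at Week 0". The other success rates are also divided by attempters.

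**Sensitivity analysis.** SAP 7.1, with matching text in SAP 5.3 and 14.5.2, provides: "Missing injection success assessments for subjects withdrawing from study treatment due to issues with the autoinjector will be included in the analysis as injection failures". Assessments marked as not attempted are treated the same way for those subjects. The analysis covers the primary endpoint only and is run only if such withdrawals occur.

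**The concern.** The screen-failure category runs past screening and past training. It can therefore take in a person who passed every check, was shown how to use the pen and backed out because of the pen. Such a person is informative about the device, and the study aims to describe use by people representative in dexterity, cognitive ability and device experience (Protocol 4.4).

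The plan already accepts that stopping because of the autoinjector should be tested as a failure. Whether that happens depends on when the subject stops. After one attempt the subject is in the sensitivity analysis. Before the first attempt, for the same reason, the subject is in no device analysis at all. Leaving such subjects out can only hold the rate up, never lower it. Each label group is reported on its own, so a few people matter more in the group of 50.

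**Working it through.** **1. Follow one subject through the rules.** The subject is eligible, trained at Visit 2, and declines because of the pen.

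- Protocol 5.4 and SAP 14.5.1: Visit 1 procedure done, no attempt, so a screen failure.
- SAP 4: no attempt, so not in All Subjects (Safety).
- SAP 7.1 and 7.2: not an attempter at Week 0, 4 or 8, so in no denominator.
- SAP 7.1 sensitivity analysis: outside the SAP 7 population, and not a withdrawal from treatment because treatment never began.
- Shell TAB_INJ2: it has a 'Not attempted' line at Week 0, but it is built on All Subjects (Safety), so that line can hold only someone who attempts later.
- What remains: Table 6.2 (screen failures), the 'Not Treated' columns of Tables 6.3 and 6.11, and Listing 1 (reasons for screen failure).

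**2. Reproduce the plan's own figures.** Protocol 9.2.1: 150/0.95 = 157.9, rounded up to 158. With 30% screen failure, 225 × 0.70 = 157.5, consistent with about 225 screened. The plan thus allows for 225 − 158 = 67 screen failures, with which any non-starters would be pooled. All 22 exact intervals in Protocol 9.2.2 reproduce. For example, 98/100 gives 93.0 to 99.8 (printed 93, 100).

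**3. Size.** The documents give no count of non-starters, so k is an assumption. With x successes among n attempters, adding k non-starters as failures gives x/(n + k). With N = n + k, the Clopper-Pearson limits are the 0.025 quantile of Beta(x, N − x + 1) and the 0.975 quantile of Beta(x + 1, N − x). I take n as the planned 100 (pictogram) and 50 (standard label). The observed success rates, 98% and 96%, are also assumptions.

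| Observed | k = 0 | k = 1 | k = 2 | k = 3 |
|---|---|---|---|---|
| 98/100 | 98.0% (93.0, 99.8) | 97.0% (91.6, 99.4) | 96.1% (90.3, 98.9) | 95.1% (89.0, 98.4) |
| 49/50 | 98.0% (89.4, 99.9) | 96.1% (86.5, 99.5) | 94.2% (84.1, 98.8) | 92.5% (81.8, 97.9) |
| 96/100 | 96.0% (90.1, 98.9) | 95.0% (88.8, 98.4) | 94.1% (87.6, 97.8) | 93.2% (86.5, 97.2) |
| 48/50 | 96.0% (86.3, 99.5) | 94.1% (83.8, 98.8) | 92.3% (81.5, 97.9) | 90.6% (79.3, 96.9) |

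At 98% observed and k = 3, the estimate falls by 98.0 − 95.1 = 2.9 points in the larger group and by 98.0 − 92.5 = 5.5 points in the smaller. Three in each group would make 6 people, against 158 − 150 = 8 dropouts allowed for in the whole study, so k = 3 in both groups is a generous upper case.

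**The case against.** The case against is substantial, and much of it stands.

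- **Use failures are largely captured.** A reader might infer that anyone who cannot work the pen is lost. The documents do not support that. TAB_INJ2 has error categories for a cap that is not or cannot be removed, a needle guard that cannot be pushed down and a device that does not activate. The observer checklist in TAB_INJ3 has a code for steps not completed or needing intervention. Such a subject would ordinarily be a failed attempt inside the denominator. A caregiver may also inject. The gap is confined to people who never attempt, although neither document defines an attempt, so sites draw that line.
- **The SAP is not breaking its own promise.** A reader might infer that the sensitivity analysis was meant to include never-starters. Its wording covers withdrawals from treatment and does not mention them. Extending it follows its logic, but it is an extension.
- **The subjects do not vanish.** They appear in the screen-failure displays, and Protocol 5.4 calls for screen-failure details. Whether the recorded reasons separate device refusal from other causes cannot be judged, because the case report form is not in the documents.
- **The choice is disclosed.** Enrolment is consistently defined by a first attempt, the denominators are stated, and the study is descriptive with no threshold.

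What survives is the unequal treatment of one reason according to its timing, with an effect in one direction only.

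**Conclusion.** The point holds for eligible, trained subjects who never attempt because of the autoinjector. They are outside All Subjects (Safety), every success rate and the sensitivity analysis, and appear only in displays pooled with other screen failures.

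The direction is certain: counting them lowers the rate whenever there is at least one. The size is not known. On the assumption of 1 to 3 per label group and 98% observed success, the estimate falls to between 97.0% and 95.1% at 100 subjects, and to between 96.1% and 92.5% at 50. With none, nothing changes.

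It would go too far to say that the reported rates are inflated, or that the 30% screen-failure allowance contains device refusals. Nothing in the documents shows that any such subject exists. No hypothesis test or success criterion is affected. This is a gap in a sensitivity analysis and its reporting, and it does not make the primary analysis wrong.

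**What to change.** Keep the primary analysis, its denominator and All Subjects (Safety) as they are, and make these changes in the SAP:

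1. Using the recorded screen-failure reasons, identify subjects who were eligible and trained at Visit 2 but did not attempt. Report their number and reasons by label beneath Tables 7.1 and 7.2, including when the number is zero. Label follows from country (SAP 5.1 and 5.4.2), so it needs no new data.
2. In SAP 7.1 and 5.3, and the parallel text in 14.5.2, extend the Week 8 sensitivity analysis to count those whose reason is the autoinjector as failures. Let their presence trigger the analysis, which now runs only if there are device-related withdrawals.
3. Add to SAP 7 an explicit exception: this sensitivity analysis uses All Subjects (Safety) plus these subjects. Without it, SAP 7 would still shut them out.
4. Optionally, add a matching Week 0 rate, labelled as a new supportive analysis, since SAP 7.1 covers only the primary endpoint.

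The SAP introduction speaks of recruitment in the past tense, so the fix relies on data already collected and not on a new Protocol 5.4 definition or a new form field. If the recorded reasons cannot identify these subjects, the report should say so. The cost is minor programming, some SAP wording and a possibly slightly lower sensitivity rate.
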